#### Exploratory outcomes

• Treatment satisfaction prior to and after nivolumab treatment initiation and health related quality of life (HR-QoL) outcomes.

*Interim analysis:* There will be three interim analyses conducted in accordance with the scientific committee of the study.

**Sample Size/Power:** The sample size calculation is based on the primary outcome of the study and has been calculated assuming a 40% DFS rate after two years of follow-up and with an absolute precision of

7% for a sample size of 314 patients (accounting for a 10% drop-out rate). These calculations are based on assumptions from the CheckMate577 trial.

**Limitations/Strengths:** Although all possible measures will be taken to ensure quality and robustness of the data collected, there are some limitations that are inherent to the observational nature of this study including selection bias, attrition bias, and variability in local treatment practices, guidelines, and data quality across sites. Notably, selection bias due to non-consent will be mitigated by providing clear information to patients and physicians on the importance of the study and low burden of participation. Furthermore, the use of a large diverse sample of patients and prescribers from the US and Germany will contribute to the generalizability of the results. The site selection process will ensure that the sites participating are representative of the US and German landscape of EC or GEJC treatment.

Findings from this study will help support results from previous clinical trials and generate real-world effectiveness data in patients initiating nivolumab for the treatment of EC/GEJC. This study will provide a better understanding of the demographics, patterns of care, and clinical outcomes of patients with EC/GEJC treated with nivolumab in routine clinical practice and will be used to inform key stakeholders, patients, healthcare practitioners, guideline committees, and regulatory authorities.

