## 4 STATISTICAL ANALYSIS

## 4.1 Statistical Analysis Methods

## 4.1.1 General Aspects

This study is purely descriptive, and no formal hypotheses will be tested. An overview of planned statistical analyses is provided in Sections 4.1.1 to 4.1.4. A standalone statistical analysis plan (SAP) will describe in detail all planned statistical analyses to be performed for this study.

The SAP will include tables, listings, figure shells to be populated during the interim and final data analyses, and details of changes in the planned analysis post-protocol finalization if applicable. It will also provide a description of the methods to deal with missing data, censoring, and procedures to control for potential sources of bias and their influence on the results.

All analyses will be conducted in accordance with the study objectives, SAP, and applicable guidelines. Statistical methods will be driven, in part, by the final sample size and the number of events. Results will be rounded to one decimal place; therefore, percentages may not always add up to 100. Standard deviation and 95% CIs will be calculated when relevant. The statistical analyses will be performed using SAS enterprise 7.1 or above, or SAS 9.4 or above. All patients who meet eligibility criteria will be included in the analysis data set.

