## 4.1.2 Analysis Plan for Primary Objective

The primary outcome of this study, DFS, will be estimated and plotted using the KM estimator for up to 42 months follow-up.

• Median DFS and the corresponding two-sided 95% CIs will be estimated.

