## 4.2 Sample Size

The sample size calculation is based on the primary outcome of the study and has been calculated assuming a 40% DFS rate after two years of follow-up and with an absolute precision of 7% for a sample size of 314 patients (to account for 10% drop-out). These calculations are based on assumptions from the CheckMate577 trial.

DFS rate (%)	Absolute precision (%)	Ν	N (Considering 10% drop-out rate)
	6%	685	754
20%	7%	504	555
	8%	385	424
	6%	526	579
30%	7%	387	426
	8%	296	326
40%	6%	386	425
	7%	285	314
	8%	217	239
50%	6%	268	295
	7%	197	217
	8%	151	167

Table 7: Sample Sizes and Absolute Rates (%)

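### Table 7's drop-out column adds 10% to N instead of dividing by 0.90, so 314 enrolled allows for about 9.2% drop-out relative to N = 285, not 10%; the practical effect is negligible

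*Protocol*

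**What the plan says.** Protocol section 4.2 sizes the study on precision at an assumed two-year DFS rate of 40%, with an "absolute precision of 7% for a sample size of 314 patients (to account for 10% drop-out". The synopsis, under Sample Size/Power, gives the same total: "7% for a sample size of 314 patients (accounting for a 10% drop-out rate". Table 7 has one column headed N and one headed "N (Considering 10% drop-out rate". In the row for a 40% DFS rate and 7% precision these read 285 and 314. The inflation formula is not written out.

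No power calculation is involved, since section 4.1.1 states: "This study is purely descriptive, and no formal hypotheses will be tested". Section 4.2 gives no confidence level; the nearest statement is in section 4.1.2: "Median DFS and the corresponding two-sided 95% CIs will be estimated".

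**The concern.** A drop-out rate is ordinarily a share of the patients enrolled. To have N left after a share d is lost, one enrols N/(1 − d). Multiplying N by 1 + d gives a smaller number, and the patients who remain then fall below N. The protocol prints 285, 10% and 314 together, and on that reading the three do not fit.

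The figure affected is the headline planned size, up to which section 3.1 has physicians enrol. Section 5.1, under attrition bias, links loss to follow-up to the risk of missing the target precision. The drop-out allowance is the sample-size safeguard against that risk, so its label should match what it provides.

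**Working it through.** **Inputs.** The N and drop-out columns of Table 7 and the 10% drop-out rate (section 4.2; the 10% is repeated in the synopsis). For the check on N: a rate of 40% and precision of 7 points (section 4.2), and a two-sided 95% level, which is an assumption carried over from section 4.1.2.

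**1. Reproducing the plan's figure.** 285 × 1.10 = 313.5, rounded up to 314. N × 1.10 rounded up returns all 12 printed entries exactly. N/0.90 rounded up returns none of them.

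| DFS rate | Precision | N | Printed (= N × 1.10, rounded up) | Left after 10% loss | N/0.90, rounded up | Shortfall |
|---|---|---|---|---|---|---|
| 20% | 6% | 685 | 754 | 678.6 | 762 | 8 |
| 20% | 7% | 504 | 555 | 499.5 | 560 | 5 |
| 20% | 8% | 385 | 424 | 381.6 | 428 | 4 |
| 30% | 6% | 526 | 579 | 521.1 | 585 | 6 |
| 30% | 7% | 387 | 426 | 383.4 | 430 | 4 |
| 30% | 8% | 296 | 326 | 293.4 | 329 | 3 |
| 40% | 6% | 386 | 425 | 382.5 | 429 | 4 |
| 40% | 7% | 285 | 314 | 282.6 | 317 | 3 |
| 40% | 8% | 217 | 239 | 215.1 | 242 | 3 |
| 50% | 6% | 268 | 295 | 265.5 | 298 | 3 |
| 50% | 7% | 197 | 217 | 195.3 | 219 | 2 |
| 50% | 8% | 151 | 167 | 150.3 | 168 | 1 |

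In every row the number left after a 10% loss is below the N beside it.

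**2. The chosen row.** 314 × 0.90 = 282.6, which is 2.4 below 285. The drop-out that 314 can absorb while leaving 285 is 1 − 285/314 = 9.2%. Allowing for 10% would take 285/0.90 = 316.7, so 317.

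**3. Effect on precision.** Half-width varies as 1/√n. Taking the table at its word that 285 gives 7.00 points, 282.6 gives 7.00 × √(285/282.6) = 7.03 points.

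**4. Does this put the 7% target out of reach?** The usual normal-approximation size for a proportion is z²p(1 − p)/d². With z = 1.96, p = 0.40 and d = 0.07 this is 3.8416 × 0.24/0.0049 = 188.2, so 189, or 189/0.90 = 210 with drop-out. The 283 patients who remain would give 1.96 × √(0.24/283) = 0.057, about ±5.7 points. So 285 does not follow from the stated inputs by this formula. The N column also rises as the rate falls from 50% to 20% (268 to 685 at 6% precision), although p(1 − p) is largest at 50%.

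**The case against.** The case for leaving the table alone has four parts.

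- **Size.** The gap in the chosen row is 2.4 patients, precision is stated to a whole per cent, and the 10% is itself a planning guess. This stands, and it is why the point is minor.
- **Convention.** Adding 10% to N is a common shortcut, and the protocol neither writes out the formula nor calls 285 an evaluable number. It is true that reading drop-out as a share of those enrolled is an inference. But if a margin of 10% of N was meant, the column heading and both text statements still need rewording.
- **Analysis.** Patients lost to follow-up are not removed. Section 3.1 censors them at their last record or assessment, section 4.1.2 uses Kaplan-Meier, and section 4.1.1 analyses all eligible patients. This stands, so 7.03 points is an upper bound on the effect on the table's scale.
- **Mitigation.** Section 5.1 acknowledges attrition and allows longer enrolment or more patients per site. That covers recruitment and conduct; it does not make the column match its label.

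A reader might infer that every figure in the column is too low in absolute terms, or that 314 patients cannot deliver ±7%. The protocol does not support either. The entries are low only relative to the table's own N. Against the standard formula, at an assumed two-sided 95% level, 314 is more than the chosen row needs.

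**Conclusion.** The point holds as a minor arithmetic correction. The drop-out column is a uniform N × 1.10 and does not allow for 10% drop-out among those enrolled. Relative to Table 7's N, the entries are 1 to 8 patients short; for the planned size the gap is 3 enrolled patients, about 1%.

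This rests on two readings: that drop-out means a share of those enrolled, and that N is the number meant to remain. It does not depend on how N was obtained, since the same step would understate enrolment for any N. How N was derived is a separate and larger question, and nothing here should be taken as confirming 285.

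**What to change.** Leave the enrolment figure at 314. In section 4.2 and in the synopsis, replace the 10% statement with one of two accurate ones: that 314 allows for about 9.2% drop-out relative to N = 285, or that about 283 patients are expected to remain at 10% drop-out.

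Recompute the last column of Table 7 as N/0.90, rounded up. With the current N the values are those in the table above, 317 for the chosen row. If the N column is re-derived, compute the drop-out column from the new N at the same time, so that 12 new figures are not issued on an unexplained base.

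The cost is two sentences and one table column. No patients are added and the analysis does not change.

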## 5 STUDY LIMITATIONS/STRENGTHS

### 5.1 Study Limitations

Although all possible measures will be undertaken to ensure quality and robustness of the data collected, some limitations are inherent to the observational nature of this study that should be acknowledged. Potential limitations and proposed strategies to address them are described in the following sections.

#### Selection bias

The target population, i.e., the entire group of individuals from which this study will conduct research in and draw conclusions from is the population of patients with early-stage EC or GEJC initiating adjuvant nivolumab treatment in real-world settings in the US or Germany. The following selection biases may compromise the representativeness of the target sample population.

Selection bias due to non-consent will be mitigated by providing clear information to physicians and patients on the importance of the study and the absence of burden for them. Physicians may also be inclined to select their "best" patients for the study, which could affect the representativeness of the study sample. To prevent this, clear instructions and methodological patient sampling will be provided to physicians who will be asked notably to include proposed enrollment in the study to all eligible patients and include all consecutive patients in the study.

The extent of the selection bias will be monitored via the maintenance of an enrollment log at the site, which will anonymously list all eligible patients, consenting status and characteristics, and inform the implementation of mitigation strategies if threats to representativeness are observed.

#### Attrition bias

In a prospective observational study, patients who are lost to follow-up or withdrawn from the study are the main source of attrition bias This bias may compromise sample representativeness and impact the interpretation of the results if there are significant differences in baseline characteristics or outcomes between patients that remain in the study and those who are lost to follow-up. If the proportion of patients lost to follow-up is non-negligible, the target precision for the primary outcome may not be reached and impact the interpretation of the findings.

To prevent this risk and minimize its potential impact, all efforts will be made to collect data from the closest previous visit and physicians will be encouraged to contact the patient to receive survival information and the vital status of patients lost to follow-up or who withdrawn from the study. A discontinuation case report form will be provided to physicians to document the reasons for discontinuation in the study.

### Hawthorne effect

Participation in an observational study may influence physicians' behaviors and adjust their practice regarding nivolumab treatment and EC/GEJC patient management. The potential for this bias has been acknowledged and, in this study, only incident (new) users of nivolumab will be included and no comparison will be made with prevalent nivolumab users.

#### Measurement error and misclassification

Clear information and definitions of the variables measured will be provided to limit the risks of measurement errors and misclassification of study outcomes. However, as this study is observational, non-interventional and aims at describing routine clinical practice, it is anticipated that some measurement errors may occur as tools used to assess patients may vary across treating physicians, sites, and countries. Notably, disease progression and recurrence measurements may particularly be prone to measurement errors as various methods may be used to assess these outcomes for example not all physicians may use Response Evaluation Criteria in Solid Tumors1.1 criteria to assess disease progression.

#### Missing data

As is the nature of non-interventional studies, reporting of outcomes is voluntary and data are collected according to routine clinical practice; therefore, not all patients may complete PRO assessment that missing data may occur. However, every effort will be implemented to minimize the impact of missing data in the study design and the conduct of the study. For these purposes the following strategies will be implemented:

- Collecting only variables that addressed the study objectives to minimize site/patient reporting burden
- Including "not applicable" or "not done" on eCRFs to differentiate these from truly unknown values
- Standardizing the data abstraction form across sites
- Ensuring that sites and data abstractors are properly trained on data collection
- Setting reporting windows around pre-specified target time point
- Checking for patterns of missingness and addressing any issues through targeted operational strategies
- Implementing direct-to-patient strategies to facilitate capture of patient-reported information

Sensitivity analysis will be performed to evaluate the impact of missing data on the study outcomes and any impact of missing data on the interpretation of the results will be discussed in the final study report.

#### **Risk of under-recruitment**

The precision of the estimates and interpretation of the results might be compromised in case of under-recruitment. This risk may occur as patient enrollment will start a limited amount of time after approval of nivolumab in patients with EC or GEJC. This risk will be mitigated by close monitoring of patients' enrollment and if necessary, by increasing the enrollment period or the maximum number of patients by site.

Overall, the impact that potential biases will have on the study results is currently unknown. Still, each potential source of bias will be evaluated descriptively, assessed by sensitivity analyses, and discussed in the reports.

## 5.2 Study Strengths

#### **Real-world data**

This is the first study collecting real-world data conducted in the US or Germany among patients with EC or GEJC who start nivolumab adjuvant therapy for the first time. The results of this study will help support findings from previous clinical trials and provide a better understanding of the demographics, patterns of care, and clinical outcomes of patients with EC/GEJC treated with nivolumab in routine clinical practice. This study will be critical to inform key stakeholders, patients, healthcare practitioners, guideline committees, and regulatory authorities.

#### Generalizability of study results

Patients will be treated as per local regulations and standards of care in real-world settings. The site selection process will ensure that the sites participating are representative with regard to the US or German landscape of EC or GEJC treatment. This study has been designed with minimal selection criteria to broaden the segment of patients with EC or GEJC and reach a high level of external validity.

# 6 STUDY CONDUCT

This study will be conducted in accordance with International Society for Pharmacoepidemiology Guidelines for Good Pharmacoepidemiology Practices and applicable regulatory requirements.

Real-world data are needed to generate real-world evidence to complement those obtained from RCTs and to demonstrate effectiveness in the studied population and in patient subgroups (e.g., specific histology, by country). Additionally, real-world evidence has been used to characterize levels and patterns of use (e.g., dosing, regimen, indication, treatment rationales, modification in relation to management of AEs, alone, sequentially, or in combination with other drugs). Real-world data tend to be more inclusive than RCT data due to less restrictive patient inclusion criteria (e.g., age, prior treatment, comorbidities, frailty) and, if follow-up is sufficient, can be a longer-term approach to understanding the impact of a drug in each target population. Therefore, data collected through prospective observational studies can be used to meet the requirements of prescribers, regulators, or payers for ongoing access to novel therapeutics.

The central aims of the study are descriptive, and are designed to capture to describe the outcomes, patient characteristics, safety profile, and treatment patterns in adult patients with EC or GEJC who start a new systemic treatment with nivolumab for the first time, and among other subgroups of interest (e.g., line of therapy, histology, country-specific) or treatment patterns (e.g., prior adjuvant therapies). Remote or on-site data monitoring will be conducted during the study to examine compliance with the protocol and adherence to the data collection procedures. There will be regular communication with all sites to assess recruitment progress and address any issues as they arise. Edit checks, described in the

Data Management Plan, and tested prior to starting data entry process, will be defined to ensure validity of the database with a focus on missing, implausible, or inconsistent data. The SAP will be prepared and approved prior to database lock. Data monitoring will close at each site after the completion of the follow-up assessment of the last patient, entry of all data, and resolution of all

outstanding monitoring issues and data queries. The database will then be locked and transferred to statisticians for analysis.

## 6.1 Ethics Committee Review and Informed Consent

### 6.1.1 Ethics Committee Review

The investigator must ensure that the required approvals from ethics committees, independent review committees, regulatory authorities, and/or other local governance bodies are obtained before study initiation at the site.

## 6.1.2 Informed Consent

In accordance with local regulations, subjects should provide written consent (e-consent) before enrollment into the study. Investigators must ensure that patients, or, in those situations where consent cannot be given by patients, their legally acceptable representatives, are clearly and fully informed about the purpose of the study, potential risks, the patient's rights and responsibilities when participating in this study. If local regulations do not require an informed consent document to be signed by the patient, the site staff should document key elements of the informed consent process in the patient's chart.

Patients may withdraw from the study at any time at their own request, or they may be withdrawn at any time at the discretion of the investigator or sponsor for safety, behavioral, or administrative reasons. In any circumstance, every effort should be made to document patient outcome, if applicable. The investigator would inquire about the reason for withdrawal and follow-up with the patient regarding any unresolved adverse events.

If the patient withdraws from the study, and also withdraws consent for disclosure of future information, no further evaluations should be performed, and no additional data should be collected. The sponsor may retain and continue to use any data collected before such withdrawal of consent.

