routinely collected during disease management in clinical practice. This study is strictly observational, and prescriptions of nivolumab will be at the sole discretion of the treating physician. The overall study duration will be up to 42 months with an enrollment period of 18 months. Data will be collected by sites at Day 0 (baseline) and month 3 (M3), M6, M9, M12, M18, M24, M30, M36, and M42. Follow-up time for the first patient in will be up to 42 months and a minimum of 24 months for the last patient in. Patients will be followed until the end of study period, death, lost to follow-up, or study withdrawal, whichever comes first.

**Study Population:** Adult subjects diagnosed with early-stage EC/GEJC initiating nivolumab treatment per the clinical care recommendation of their treating physician and meeting the following inclusion criteria and none of the exclusion criteria will be eligible to participate in the study:

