Physicians will be asked to enroll eligible patients consecutively until the total expected study sample size is reached or the end of the enrollment period (whichever occurs first). The enrollment period is anticipated to last approximately 18 months. The follow-up time will vary between patients due to the nature of the study with ongoing enrollment; patients will be followed for up to 42 months for the first patient in and up to 24 months for the last patient in. Patients will be followed until the end of study period, death, lost to follow-up, or withdrawal, whichever comes first. Patients will be censored at last record or assessment for those lost to follow-up.

Assessment schedules will be performed according to routine local clinical practice. Data collection and data entry by sites will start at Day 0 (baseline, i.e., the day of nivolumab initiation), and at the following months with a time window of +/- 15 days: months 3, 6, 9, 12, 18, 24, 30, 36, and 42 counted relative to treatment initiation (two and 3.5 years after nivolumab initiation for the first and last patient in, respectively). As this is a non-interventional study, no visits or measurements will be made mandatory by the protocol, and data collection at these prespecified timepoints will only take place if the patient visits the site as per standard of care. Investigators or qualified research staff should collect data from the visit nearest to the time point.

Sites will receive fees to compensate for the time spent for data collection and entry into eCRFs. Since the study is intended to reflect usual clinical practice, physicians will not be required to perform any mandatory patient assessments or laboratory tests that they would not ordinarily do in treating their patients. This protocol requires that sites submit all relevant documentation to their respective institutional review board (IRB) or Ethics Committee (EC) and obtain approval or acknowledgment of notification, depending on the local requirements. Participating patients must provide written informed consent prior to study commencement, and they have the right to withdraw from the study at any time. This study will be conducted with support of a clinical research organization (CRO).

An overview of study design and data collection is shown in Figure 1.

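### The synopsis and section 3.1 end follow-up at any withdrawal, while section 6.1.2 stops data collection only when disclosure consent is also withdrawn; recurrences that could be collected may be lost

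*Protocol*

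**What the plan says.** Four places in the protocol bear on what happens after a patient withdraws.

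- **Synopsis, Study Design:** "Patients will be followed until the end of study period, death, lost to follow-up, or study withdrawal, whichever comes first".
- **Section 3.1:** "Patients will be followed until the end of study period, death, lost to follow-up, or withdrawal, whichever comes first". The censoring sentence that follows covers one group only: "Patients will be censored at last record or assessment for those lost to follow-up". Withdrawal is not named in it.
- **Section 6.1.2:** collection stops under a double condition, "If the patient withdraws from the study, and also withdraws consent for disclosure of future information, no further evaluations should be performed". Just before that, for withdrawals generally: "In any circumstance, every effort should be made to document patient outcome, if applicable". Withdrawal need not come from the patient: "they may be withdrawn at any time at the discretion of the investigator or sponsor for safety, behavioral, or administrative reasons".
- **Section 5.1, Attrition bias:** "physicians will be encouraged to contact the patient to receive survival information and the vital status of patients lost to follow-up or who withdrawn". This is encouragement, not a requirement. It covers survival and does not mention recurrence. The same section provides a discontinuation case report form.

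Section 4.2 allows for 10% drop-out and does not divide it between withdrawal and loss to follow-up.

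**The concern.** A patient who leaves the study but does not withdraw disclosure consent is out of follow-up under section 3.1 and still to be documented under section 6.1.2. Two sites can each follow the protocol and collect different data on the same kind of patient.

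The study reads its outcomes from medical files, so recurrence and death in such a patient usually remain obtainable without a visit. A site that stops at section 3.1 does not abstract them. Section 5.1 might recover a death, but it does not ask for the recurrence, and recurrence is a component of the primary outcome.

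Censoring at withdrawal is harmless to a Kaplan-Meier estimate when withdrawal is unrelated to risk. It is not harmless when patients leave because they are declining, or because they are doing well. Withdrawal by the investigator or sponsor for safety reasons is one route by which leaving could be linked to prognosis. DFS, DMFS and OS are all exposed. Section 5.1 itself treats withdrawn and lost patients as the main source of attrition bias.

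**Working it through.** **The passages side by side, for a patient who withdraws but keeps disclosure consent**

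| Place | Follow-up after withdrawal | Recurrence collected? | Vital status collected? |
|---|---|---|---|
| Synopsis and 3.1 | Ends | No | No |
| 6.1.2 | Not barred; outcome to be documented | Yes, if outcome includes recurrence | Yes |
| 5.1 | Contact encouraged | Not named | Encouraged |

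The first row cannot be met together with the second.

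**The plan's own drop-out figure.** Section 4.2 inflates 285 patients to 314: 285 × 1.10 = 313.5, rounded up to 314. The 10% is the only stated figure that bears on withdrawal.

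**Size of a possible bias in 24-month DFS**

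Inputs from section 4.2: DFS of 40% at 24 months; 10% drop-out.

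Assumptions that are not in the protocol: exponential event and withdrawal times; the whole 10% is withdrawal by month 24 (an upper value, since drop-out also includes loss to follow-up); the event hazard is multiplied by *k* after withdrawal.

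1. Event hazard before withdrawal: h = −ln(0.40)/24 = 0.03818 per month.
2. Withdrawal hazard w, from w/(w+h) × [1 − exp(−24(w+h))] = 0.10. This gives w = 0.00681 per month. For 5% withdrawal, w = 0.00329.
3. If every withdrawn patient is censored at withdrawal, the Kaplan-Meier curve estimates exp(−24h) = 40.0%, whatever *k* is.
4. The true proportion event-free at 24 months is exp(−24(h+w)) + ∫₀²⁴ w·exp(−(h+w)u)·exp(−kh(24−u)) du. The first term is 0.3397 for 10% withdrawal and 0.3696 for 5%.

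| Withdrawn | k | Integral | True DFS | Kaplan-Meier minus truth |
|---|---|---|---|---|
| 10% | 0.5 | 0.0770 | 41.7% | −1.7 points |
| 10% | 1 | 0.0603 | 40.0% | 0 |
| 10% | 2 | 0.0390 | 37.9% | +2.1 points |
| 10% | 3 | 0.0270 | 36.7% | +3.3 points |
| 5% | 2 | 0.0198 | 38.9% | +1.1 points |

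A separate simulation of 400,000 patients with about 10% withdrawn gave the same picture: 40.0% against a true 37.8% when the hazard doubles, 40.0% against 41.7% when it halves, and 39.9% against 39.9% when it is unchanged.

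**The case against.** **The passages can be read together.** On this view the synopsis and section 3.1 describe the end of scheduled follow-up, and sections 6.1.2 and 5.1 say what is still done afterwards. That is a fair reading of intent, and it means the protocol does not simply throw the data away. But section 3.1 has no cross-reference to 6.1.2, and scheduled abstraction is how recurrence reaches the database. An unspecified effort to document outcome plus optional contact about survival does not replace it.

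**Censoring belongs to the statistical analysis plan.** Section 4.1.1 says so, and detailed censoring rules are not part of this point. What remains is which data sites collect. The analysis plan cannot restore recurrences that were never abstracted.

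**The shifts are small and conditional.** This stands. All the illustrated shifts are below the 7-point precision target, and 10% is a generous withdrawal rate. The figures also treat everyone as recoverable, although patients who withdraw disclosure consent cannot be followed under any wording.

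**Stronger readings that the documents do not support.** A reader might infer that the plan certainly biases DFS and OS. It does not: there is no bias if risk is unchanged after withdrawal, and the direction depends on how risk changes. A reader might also infer that deaths found after withdrawal would count as events while survivors keep their withdrawal date, which would push OS down. No passage says this. Table 2 censors OS at the date a patient was last known to be alive, and section 5.1 asks for vital status, not for deaths alone. Uneven capture could happen in practice, but it is not a rule of this plan.

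**Conclusion.** The contradiction is real and should be resolved. Follow-up ends at any withdrawal in the synopsis and section 3.1. In section 6.1.2 collection stops only when disclosure consent is also withdrawn. Section 5.1 closes the gap only partly, for survival and on a voluntary basis.

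The consequence is a risk of bias, not an established one. Under the assumptions set out above, with 10% withdrawal, 24-month DFS would be misstated by +2.1 points if the hazard doubles after withdrawal and by −1.7 points if it halves. At 5% withdrawal with a doubled hazard the error is +1.1 points. The protocol gives neither a withdrawal rate nor any information on risk after withdrawal, so the actual size and direction are unknown. The same mechanism applies to DMFS and OS, but no size was worked out for them here.

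The shifts are modest beside the 7-point precision, but unlike sampling error they do not shrink as patients are added. The point is worth correcting because the correction is cheap and the lost data cannot be recovered later; it does not threaten the study as a whole.

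**What to change.** 1. In the synopsis and section 3.1, replace withdrawal as an end of follow-up with withdrawal of consent to disclose future information, and cross-refer to section 6.1.2.
2. For all other withdrawals, and where the consent and local rules allow, continue abstracting recurrence, subsequent therapy and vital status (dead or alive, with the date) from the medical record at the scheduled timepoints.
3. Bring the attrition paragraph of section 5.1 into line, so that it names recurrence as well as survival.
4. On the existing discontinuation form, record which type of withdrawal applies.

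Detailed censoring rules can stay in the statistical analysis plan.

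**Cost:** a few sentences, one item on a form that is already planned, and some more chart abstraction for a small number of patients. No visits, tests or patients are added. The consent wording was not available for this review, so whether it already permits continued abstraction in both countries has to be checked first.
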